## 6.2 DURING TREATMENT PROCEDURES BY VISIT

Once eligibility has been confirmed, the subject will be randomized to receive study treatment. Visit dates and windows must be calculated from Day 0.

### 6.2.1 DAY 0

The following evaluations will be performed on Day 0 **prior to study treatment**:

- Determination of eligibility per Inclusion/Exclusion Criteria
- Review of concomitant medications and adverse events

- Randomization
- Patient Reported Outcomes
- Targeted physical assessment
- Vital signs
- Urine pregnancy test
- Whole blood and serum for immunologic assay including miRNA profile
- Cervical colposcopy
  - Photographs during colposcopic examinations of the vagina and/or cervical areas should be obtained if lesions are identified.
- Cervical cytology and ThinPrep® for cervical HPV type
  - Collect menstrual cycle status and recent gynecologic history
- OP rinse, vulvar, vaginal and intra-anal swabs
- Vulvoscopy
- Vulvar lesion photography of the qualifying lesion(s)

Study treatment will be administered and the following evaluations will be performed on Day 0 **after study treatment**:

- Post treatment AE and injection site reaction assessment within 30-45 minutes after study treatment
- Distribute Participant Diary (PD)
- Distribute 1 box of imiquimod and the imiquimod dosing log (for subjects in the imiquimod arm)

Download EP data from device within 24 – 48 hours of study treatment

### **6.2.2 8-14 DAYS POST DOSE 1 PHONE CALL**

- Review Adverse Events
- Patient Reported Outcomes
- Review Day 0 PD
  - After completing a review of PD and post treatment injection assessment with the subject on the phone, the Investigator or study personnel will determine whether an office visit is needed for further evaluation.

### **6.2.3 WEEK 4 (± 7 DAYS):**

The following study evaluations will be performed at Week 4 **prior to study treatment**

- Review of concomitant medications and adverse events
- Targeted physical assessment
- Vital signs

- Review imiquimod dosing log and usage (accountability of returned product) for subjects in the imiquimod arm
- Urine pregnancy test
- Vulvar swab
- Vulvoscopy
- Vulvar lesion photography of the qualifying lesion(s)

The following study evaluations will be performed at Week 4 **after study treatment**:

- Post treatment injection site reaction assessment within 30-45 minutes after study treatment
- Patient Reported Outcomes
- Distribute PD
- Distribute 1 box of imiquimod and the imiquimod dosing log (for subjects in the imiquimod arm)

Download EP data from device within 24 – 48 hours of study treatment

#### **6.2.4 8-14 DAYS POST DOSE 2 PHONE CALL**

- Review Adverse Events
- Patient Reported Outcomes
- Review Week 4 PD
  - After completing a review of PD and post treatment injection assessment with the subject on the phone, the Investigator or study personnel will determine whether an office visit is needed for further evaluation.

#### **6.2.5 WEEK 12 (± 7 DAYS)**

The following study evaluations will be performed at Week 12 **prior to study treatment**:

- Review of concomitant medications and adverse events
- Targeted physical assessment
- Vital signs
- Review imiquimod dosing log and usage (accountability of returned product) for subjects in the imiquimod arm
- Urine pregnancy test
- Cervical cytology and ThinPrep® for cervical HPV type
  - Collect menstrual cycle status and recent gynecologic history
- Vulvar swab
- Vulvoscopy

- Vulvar lesion photography of the qualifying lesion(s)

The following study evaluations will be performed at Week 12 **after study treatment**:

- Post-treatment injection site reaction assessment within 30-45 minutes after study treatment
- Patient Reported Outcomes
- Distribute PD
- Distribute 1 box of imiquimod and the imiquimod dosing log to subjects in the imiquimod arm

Download EP data from device within 24 – 48 hours of study treatment

#### **6.2.6 WEEK 15 (± 7 DAYS):**

The following study evaluations will be performed at Week 15:

- Review Adverse Events
- Review Week 12 Participant Diary
- Patient Reported Outcomes
- Whole blood and serum for immunologic assay including miRNA profile

#### **6.2.7 WEEK 24 (± 7 DAYS)**

The following study evaluations will be performed at Week 24 **prior to study treatment**:

- Review of concomitant medications and adverse events
- Review imiquimod dosing log and usage (accountability of returned product) for subjects in the imiquimod arm
- Targeted physical assessment
- Vital signs
- Urine pregnancy test

The following study evaluations will be performed at Week 24 **after study treatment**:

- Post-treatment injection site reaction assessment within 30-45 minutes after study treatment
- Patient Reported Outcomes
- Distribute PD

Download EP data from device within 24 – 48 hours of study treatment

### **6.2.8 WEEK 27 ( $\pm$ 7 DAYS)**

The following study evaluations will be performed at Week 27:

- Review of concomitant medications and adverse events
- Review Week 24 Participant Diary
- Targeted physical assessment
- Vital signs
- Patient Reported Outcomes
- Urine pregnancy test
- Whole blood and serum for immunologic assay
- OP oral rinse, vulvar, vaginal and intra-anal swabs
- Vulvoscopy
- Vulvar lesion photography of the qualifying lesion(s)

### **6.2.9 WEEK 38 PHONE CALL**

- Review concomitant medications and adverse events

### **6.2.10 WEEK 48 ( $\pm$ 7 DAYS)**

The following study evaluations will be performed at Week 48:

- Targeted physical assessment
- Vital signs
- Review of concomitant medications and adverse events
- Socio-Behavioral Assessment; including self-reported smoking history, self-reported exposure to second-hand smoke, self-reported alcohol intake history, contraceptive history
- Urine pregnancy test
- Whole blood and serum for immunologic assay including miRNA profile
- Cervical cytology and ThinPrep® for cervical HPV type
  - Collect menstrual cycle status and recent gynecologic history
- OP oral rinse, vulvar, vaginal and intra-anal swabs
- Vulvoscopy
- Vulvar lesion photography of the qualifying lesion(s)

- Vulvar biopsy or wide excision as per Investigator discretion:
  - All biopsy samples must be sent to the PAC for review
- Patient Reported Outcomes

#### **6.2.11 WEEK 52 (± 14 DAYS)**

Subjects will have a Week 52 consultation to discuss their biopsy results and treatment plan. The following assessments will also be performed:

- Review of concomitant medications and adverse events
- Targeted physical assessment
- Vital signs
- Patient Reported Outcomes
- Urine pregnancy test (for subjects receiving a 5th dose only)

Subjects receiving a 5th dose will have the following evaluations performed at Week 52 **after study treatment:**

- Post-treatment injection site reaction assessment within 30-45 minutes after study treatment
- Distribute Participant Diary

Download EP data from device within 24 – 48 hours of study treatment

#### **6.2.12 WEEK 74 (± 14 DAYS)**

The following study evaluations will be performed at Week 74:

- Review of concomitant medications and adverse events
- Review Week 52 Participant Diary
- Targeted physical assessment
- Vital signs
- Patient Reported Outcomes
- Urine pregnancy test
- Whole blood and serum for immunologic assay
- OP oral rinse, vulvar, vaginal and intra-anal swabs
- Vulvoscopy
- Vulvar lesion photography of the qualifying lesion(s)
- Vulvar biopsy or wide excision as per Investigator discretion:

- All biopsy samples must be sent to the PAC for review

### **6.2.13 WEEK 78 (± 14 DAYS)**

Subjects will have a Week 78 consultation to discuss their biopsy results and treatment plan. The following assessments will also be performed:

- Review of concomitant medications and adverse events
- Targeted physical assessment
- Vital signs
- Urine pregnancy test (for subjects receiving a 6th dose only)

Subjects receiving a 6th dose will have the following evaluations performed at Week 78 **after study treatment:**

- Post-treatment injection site reaction assessment within 30-45 minutes after study treatment
- Distribute Participant Diary

Download EP data from device within 24-48 hours of study treatment

### **6.2.14 WEEK 96 (± 14 DAYS)**

The following study evaluations will be performed at Week 96:

- Review of concomitant medications and adverse events
- Review Week 78 Participant Diary
- Targeted physical assessment
- Vital signs
- Patient Reported Outcomes
- Urine pregnancy test
- Whole blood and serum for immunologic assay
- Cervical colposcopy
  - Photographs during colposcopic examinations of the vagina and/or cervical areas should be obtained if lesions are identified.
- Cervical cytology and ThinPrep® for HPV type
  - Collect menstrual cycle status and recent gynecologic history
- OP oral rinse, vulvar, vaginal and intra-anal swabs
- Vulvoscopy
- Vulvar lesion photography of the qualifying lesion(s)

- Vulvar biopsy or wide excision as per Investigator discretion:
  - All biopsy samples must be sent to the PAC for review

### **6.2.15 WEEK 100 (± 14 DAYS)**

The following study evaluations will be performed at Week 100:

- Review of concomitant medications and adverse events
- Socio-Behavioral Assessment; including self-reported smoking history, self-reported exposure to second-hand smoke, self-reported alcohol intake history, contraceptive history
- Targeted physical assessment
- Vital signs
- Urine pregnancy test

## **6.3 EVALUATIONS AND PROCEDURES**

### **6.3.1 INFORMED CONSENT**

All subjects must sign the informed consent prior to any study related procedures being performed (i.e., prior to any screening activities). The informed consent documentation must be in accordance with applicable regulations and GCP. Qualified study personnel will meet with prospective study subjects, explain the study, and provide them with an informed consent form (ICF) that describes the screening tests, eligibility criteria for entering the study, study treatments and follow-up procedures, in a language understandable to the subject. Explanation of the study includes, but is not limited to, study objectives, potential benefits and risks, discomforts/inconveniences, and the subject's rights and responsibilities. The subject is then requested to sign and date the ICF. A copy of the signed informed consent documentation must be provided to the subject. The qualified study personnel will document the process of obtaining informed consent within the source record. Signed ICFs are maintained in the subject's source records and must be accessible for verification at any time.

### **6.3.2 RESCREENING OF SCREEN FAILURES**

Subjects who sign the informed consent and are assigned a subject identification number (SID) but do not meet the eligibility criteria or fall outside of the screening window will be considered screen failures. If the Investigator believes rescreening is warranted, the Investigator must contact the medical monitor to discuss.

### **6.3.3 ASSIGNMENT OF SUBJECT IDENTIFICATION NUMBERS**

Each subject who consents will be assigned a unique SID, which identifies the subject for all study-related procedures. SIDs are a combination of a up to two alpha letters study code, two alpha letter Country code, two digit site number, plus 3-digit subject number starting with 001 (e.g., VNUS01001). Once assigned, SIDs cannot be reused for

any reason. Information regarding the SID and screen date must be documented on a Screening log/system and in the Interactive Response Technology (IXRS).

Subjects meeting eligibility criteria will be randomized by a computer generated allocation schedule.

#### **6.3.4 SAFETY EVALUATIONS**

##### **6.3.4.1 PHYSICAL EXAMINATION**

A full physical examination (PE) will be conducted during screening and study discharge (Week 100). It will include an assessment of the following: general appearance, skin, head, eyes, ears, nose, and throat, and lymph nodes, and respiratory, cardiovascular, gastrointestinal, genitourinary, musculoskeletal, and neurological systems. All assessments not completed should be marked as not done.

A targeted physical assessment will be performed at other visits as determined by the Investigator or directed per subject complaints.

##### **6.3.4.2 VITAL SIGNS**

Vital signs will be measured at specified visits and will include:

- Sitting systolic and diastolic blood pressures with subject sitting at rest for at least 5 minutes before measurement
- Respiration rate
- Heart rate
- Oral temperature measured with an automated thermometer

##### **6.3.4.3 WEIGHT AND HEIGHT**

Weight will be measured at all dosing visits and at screening, and height will be measured at screening to assess BMI.

##### **6.3.4.4 MEDICAL HISTORY**

Medical history, including smoking history and gynecologic history, will be obtained at screening. All relevant (as judged by the Investigator) past and present conditions, as well as prior surgical procedures will be recorded for the main body systems.

##### **6.3.4.5 SOCIO-BEHAVIORAL ASSESSMENT**

Socio-Behavioral Assessment, including self-reported smoking history, self-reported history of exposure to second-hand smoke, self-reported alcohol intake history, self-reported recreational drug use history, self-reported history of contraceptive use and type of contraceptive if known, reproductive history, history of prior cervical dysplasia, and pregnancy history will be obtained at Screening.

At Weeks 48 and 100, socio-behavioral assessment will be performed to document any change from screening.

#### **6.3.4.6 LABORATORY EVALUATIONS**

At screening, blood samples will be taken to be tested for serum chemistry and hematology.

##### Complete blood count (CBC):

- White blood cell (WBC) count with differential
- Red blood cell (RBC) count
- Hemoglobin, Hematocrit
- Platelet count

##### Serum Chemistry:

- Glucose
- Alanine aminotransferase (ALT)
- Blood urea nitrogen (BUN)
- Creatinine
- Electrolytes (Sodium, Potassium, Chloride, Carbon Dioxide or Bicarbonate)
- Creatine Phosphokinase (CPK)

##### Urinalysis (UA):

Urine samples will be tested at screening by dipstick for glucose, protein, and hematuria. If abnormal (presence of protein, hematuria, or glucose  $\geq$  1+) a microscopic examination should be performed.

#### **6.3.4.7 PREGNANCY TESTING**

For subjects of reproductive potential, a negative spot urine pregnancy test is required at screening, and prior to each study treatment, vulvoscopy and surgical excision or biopsy.

#### **6.3.4.8 ELECTROCARDIOGRAM (ECG)**

A single 12-lead ECG will be obtained during Screening after the subject has been in a supine position for 10 to 15 minutes. The ECG should include measurements of ventricular rate, PR, QRS, QRS axis, QT, QTcb or QTcf, ST segment, T wave as well as an Investigator assessment of whether the ECG is normal or abnormal (automated interpretations of ECG should not be used). Abnormal ECGs should be interpreted as "clinically significant (CS)" or "not clinically significant (NCS)" by the Investigator.

#### **6.3.4.9 POST-TREATMENT REACTION ASSESSMENTS**

The PD will capture subject reported local and systemic events for 7 days after the study treatment.

The subject will be provided a PD and will be asked to record the following the evening of study treatment through Day 6:

- Oral temperature and time taken (before 11:59 pm)
- General symptoms of feeling unwell
- Pain and itching at injection site
- Measure redness, swelling, bruising at injection site
- Medications taken

The completed PD will be reviewed with the subject and research staff at 8 -14 Days post-dose.

The study staff will review the PD for general symptoms (e.g. malaise, fatigue, headache, nausea, and myalgia/arthritis), injection site reaction symptoms (e.g. pain, erythema and edema), medical events and medications. All reported events will be assessed for clinical significance (CS) and reported as adverse event accordingly.

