## 6. STUDY PROCEDURES AND TREATMENTS

This section lists the procedures and parameters for each planned study evaluation. The timing of each assessment is listed in the Schedule of Events Table (see [Table 1](#)).

A subject will be required to provide informed consent for use of any information collected prior to consenting and before any additional study specific procedures are performed.

Protocol waivers or exemptions will not be granted with the exception of immediate safety concerns. Therefore, adherence to the study design requirements, including those specified in the Schedule of Events Table are essential and required for study conduct.

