#### **6.6 ASSESSMENT OF CLINICAL STUDY ADVERSE EVENTS**

The injection site will be assessed by study personnel prior to and between 30-45 minutes after each study treatment. Subjects will be advised to record local and systemic AEs for 7 days after each study treatment on a PD which will be reviewed with study personnel at 8 – 14 days after dose 1 and 2, and at Weeks 15, 27, 74, and 96.

An assessment will be conducted at each visit during which subjects will be queried regarding the occurrence of any adverse events, concomitant medications new onset illness or disease, as well as contraceptive compliance. Subjects will be reminded to contact study personnel and immediately report any event that happens for the duration of the study. Unsolicited adverse events will be captured from the time of the informed consent to study discharge. These events will be recorded on the subject's CRF.

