- o A phone call will be used to review the Participant Diary (PD) with subject within 8-14 days following dose 1 and 2. The patient will be expected to bring the PD to the next visit for review.
- p PRO measures (SF-36v2™, EQ-5D-5L, WOMAN-PRO) plus two additional questions will be assessed as described in [Section 6.8](#).

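### Protocol v2.0 sets diary review at 8–14 days after dosing for every dose, but schedules review of the dose 5 and 6 diaries only at Weeks 74 and 96, nominally 22 and 18 weeks later

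*Protocol*

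**What the plan says.** Section 6.3.4.9 of version 2.0 has subjects record local and systemic events in the diary for seven days after study treatment. It then says: "The completed PD will be reviewed with the subject and research staff at 8 -14 Days post-dose". No dose is excepted. The same sentence stands in version 1.3, where the section is numbered 6.3.3.9.

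The rest of version 2.0 is more specific:

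- Section 6.6 has the diary reviewed at 8–14 days "after dose 1 and 2, and at Weeks 15, 27, 74, and 96".
- Footnote o to Table 1 provides a phone call to "review the Participant Diary (PD) with subject within 8-14 days following dose 1 and 2". It is silent on later doses; the Table 1 grid marks their diary reviews at Weeks 15, 27, 74 and 96.
- The visit lists agree with the grid. Week 74 has "Review Week 52 Participant Diary" and Week 96 has "Review Week 78 Participant Diary".
- Section 6 says which source governs: "The timing of each assessment is listed in the Schedule of Events Table".

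Doses 5 and 6 are optional and are given at Weeks 52 and 78 to Subgroups C and D only (Section 6.4). On the day of each, the staff check listed is "Post-treatment injection site reaction assessment within 30-45 minutes after study treatment". Section 6.6 also says subjects will be reminded to contact the site and "immediately report any event that happens for the duration of the study".

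**The concern.** Section 6.3.4.9 sets a time limit for a safety review, and for the last two doses the schedule leaves no visit or call that could meet it. Sites following Table 1, as Section 6 directs, would hold these diaries unreviewed for months.

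This matters because of how Sections 7.3.1 and 7.3.2 work. The site-reaction AESIs are those recorded two hours or more after treatment, so the 30–45 minute check cannot detect them. After that check, the routes left are the diary and the subject's own report. AESIs go to the sponsor within 24 hours so that further dosing can be discussed. Separately, enrollment and treatment pause if three subjects have the same related Grade 3 or 4 event. If a Grade 3 reaction after dose 5 or 6 is written in the diary and not phoned in, both mechanisms learn of it only when the diary is opened. Grade 3 erythema, induration, fever or systemic symptoms would be late for AESI reporting. Any related Grade 3 event, including site pain (an AESI only from Grade 4), would be late for the three-subject rule.

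**Working it through.** **Inputs** (version 2.0, Table 1 and Section 6.2; all windows count from Day 0):

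- Dose 3 at Week 12 ± 7 days, diary review at Week 15 ± 7 days
- Dose 4 at Week 24 ± 7 days, diary review at Week 27 ± 7 days
- Dose 5 at Week 52 ± 14 days, diary review at Week 74 ± 14 days
- Dose 6 at Week 78 ± 14 days, diary review at Week 96 ± 14 days

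**Formula.** Nominal gap = (review week − dose week) × 7. The shortest and longest gaps subtract and add the two visit windows.

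| Dose | Nominal gap (days) | Permitted range (days) | Can 8–14 days be met? |
|---|---|---|---|
| 3 | (15 − 12) × 7 = 21 | 21 − 14 = 7 to 21 + 14 = 35 | Yes, on some dates |
| 4 | (27 − 24) × 7 = 21 | 7 to 35 | Yes, on some dates |
| 5 | (74 − 52) × 7 = 154 | 154 − 28 = 126 to 154 + 28 = 182 | No |
| 6 | (96 − 78) × 7 = 126 | 126 − 28 = 98 to 126 + 28 = 154 | No |

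Check on the shortest gaps:

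- Dose 5 at its latest is day 52 × 7 + 14 = 378, and Week 74 at its earliest is day 74 × 7 − 14 = 504. The gap is 126 days.
- Dose 6 at its latest is day 78 × 7 + 14 = 560, and Week 96 at its earliest is day 96 × 7 − 14 = 658. The gap is 98 days.

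In weeks, the gap is 22 (18–26) for dose 5 and 18 (14–22) for dose 6.

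**Delay beyond day 14.** Dose 5: 154 − 14 = 140 days (112–168). Dose 6: 126 − 14 = 112 days (84–140).

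**DSMB meetings inside that delay.** If meetings are 91 days apart, which is an assumption, dose 5 gives 112/91 = 1.23 to 168/91 = 1.85 intervals, so one or two meetings. Dose 6 gives 84/91 = 0.92 to 140/91 = 1.54 intervals, so none to two.

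**Contacts in the gap.** Table 1 has no visit or call between Weeks 52 and 74, or between Weeks 78 and 96. The version 2.1 grid is the same.

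**The case against.** The strongest reply is that one loose general sentence stands against a specific and consistent schedule. Section 6 gives timing to Table 1; the grid, Section 6.6 and the visit lists agree; and sites therefore have a workable instruction. Narrowing Section 6.3.4.9 would remove the conflict. On this view, lighter follow-up after four doses is a legitimate choice, especially as Section 1.1.16 describes injection site reactions as generally mild and lasting a few days at most. All of that stands. It settles the wording, but a narrower sentence would leave the delay in place.

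A reader might infer more than the documents support, in five ways:

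- *That the contradiction is shown in version 2.1.* It is not. The version 2.1 Table 1 and footnote o keep the review times, and its change list names no edit to Section 6.3.4.9 or 6.6. But that text is not shown, and the list says unlisted administrative changes were also made.
- *That a late reaction would be graded from the diary alone.* Review is with the subject, and Weeks 74 and 96 are clinic visits with adverse event and medication review. Grading would rest on the diary plus months-old recall.
- *That the secondary endpoint on seven-day local and systemic events is compromised.* Diary entries are made as events occur, so it is little affected. The reminder to report events immediately and SAE reporting should bring most Grade 4 events to light earlier.
- *That the 30–45 minute check is a weakness peculiar to doses 5 and 6.* The same check follows every dose. What differs is the time until the next contact.
- *That the DSMB would certainly miss such an event.* The meeting count depends on assumed spacing, Section 10.4.1 allows meetings to be cancelled or added, and the dose 6 range includes zero.

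**Conclusion.** The point holds for versions 1.3 and 2.0 as a stated safety-review rule that the schedule cannot meet for doses 5 and 6: nominally 154 days (126–182) and 126 days (98–154) against 8–14 days. Version 2.1 demonstrably keeps the gap; whether it keeps the conflicting sentence cannot be confirmed. Doses 3 and 4 need clarified wording only.

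The effect is limited to a related Grade 3 reaction, after an optional dose, that is recorded but not phoned in. How many such events would occur cannot be estimated from the document. Because the Week 74 review is scheduled before dose 6, a subject's own next dose can still be informed by it; the delay bears on AESI reporting, the pausing rule and other subjects under treatment. The primary endpoint and the power are untouched. This is an optional or low-priority improvement.

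**What to change.** Extend the existing 8–14 day phone diary review to subjects who receive dose 5 or 6, in Table 1, its footnote o, Section 6.2 and Section 6.6. That places a call about Weeks 53–54 and 79–80. In Section 6.3.4.9, state that the 8–14 day review applies to doses 1, 2, 5 and 6, and that the dose 3 and 4 diaries are reviewed at Weeks 15 and 27. Check the version 2.1 wording of Sections 6.3.4.9 and 6.6 first.

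The running cost is one short call per optional dose, so at most two per affected subject, of the kind sites already make after doses 1 and 2. No new procedure or sample is needed. An added subject contact is not purely administrative, so under Section 9.9 it needs sponsor approval and an IRB-approved amendment across about 28 sites; it is best bundled with the next amendment.
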